8.2.3.3 Anticipation

The investigator is responsible for determining whether an adverse event is expected or unexpected. If the nature, severity, or frequency of an adverse event is inconsistent with the risk information of the previously described research intervention (e.g., investigator's brochure, approved instructions), it is considered unexpected. The assessment of anticipation should be based on previously observed adverse events and should not be inferred from the nature of the research intervention.

8.2.4 Timing and frequency of adverse event assessment and follow-up

The occurrence of adverse events (AEs) or serious adverse events (SAEs) should be brought to the attention of the investigator during visits to the subject receiving

medical care or for review by the monitor. All adverse events that do not meet the criteria for serious adverse events will be recorded on the appropriate case report form (CRF), including local reactions and systemic reactions. Information to be collected includes description of the event, time of onset, clinician's assessment of severity (which should only be assessed by those with training and diagnostic authority), relationship to the investigational product, expected nature, and time to resolution/stabilization of the event. All adverse events occurring during the study must be recorded, regardless of whether they are related to the study intervention. All adverse events are followed up until reasonably resolved. The medical condition at the time of screening of the subject should be considered as baseline and not reported as an adverse event. However, if the subject's condition deteriorates at any time, it should be recorded as an adverse event. Changes in the severity of adverse events should be recorded to allow for an assessment of the duration of the event at each severity level. Intermittent adverse events require the time of onset and duration of each occurrence to be recorded.

From the signing of the informed consent form to 7 days (non-serious adverse events) or 30 days (serious adverse events) after the end of the trial, the investigator should record all events that need to be reported. At each visit, the researcher should ask about adverse events/serious adverse events that occurred after the last visit. Follow up the outcome information of the event until the adverse event is resolved or stabilized. All serious adverse events should be followed up until the event is resolved satisfactorily, or the investigator considers the event to be chronic, or the subject's condition is stable.

8.2.5 Serious adverse event reporting

After receiving safety-related information from any source, researchers should immediately analyze and evaluate it, including its severity, relevance to the trial drug, etc. Suspected and unexpected serious adverse reactions should be promptly reported to the clinical trial institution and ethics committee.

8.2.6 Pregnancy report

Pregnancy that occurs during the study must be recorded and reported using the pregnancy report form. To ensure the safety of the subject, pregnancy must be reported to the principal investigator immediately and must be followed up to determine its outcome (including early termination of pregnancy) and maternal and fetal status. Pregnancy complications and termination of pregnancy for medical reasons must be reported as AEs or SAEs. Spontaneous abortion must be reported as an SAE. Any pregnancy-related SAE that occurs and comes to the attention of the investigator after the subject completes the study and is believed to be possibly related to the study drug must be reported immediately to the principal investigator. In addition, the investigator must collect information on the pregnancy of the female sexual partner of the male subject after enrollment in the study, whenever possible. Pregnancy information must be reported as described above.

9. Statistical considerations

9.1 Sample size estimation

This study is a single-arm, prospective, exploratory, single-center phase II clinical study. The sample size calculation was based on the primary study endpoint, namely, PFS assessed by the investigator.

The primary endpoint was the median PFS assessed by the investigator. Based on previous studies on radical radiotherapy for elderly esophageal cancer, the median PFS of elderly patients with locally advanced and inoperable esophageal squamous cell carcinoma after radical radiotherapy was 16 months. It was estimated that the median PFS of this study could reach 18.2 months. Using a one-sided test, $\alpha=0.05$, power=0.80, the sample size was calculated to be 41 cases. Considering the dropout rate of 20%, a total sample size of 52 subjects was required.

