survival of patients with esophageal cancer without increasing the incidence of adverse events. Combined chemoradiotherapy/radiotherapy can be recommended for the treatment of patients with esophageal cancer. In 2019, Zhai Yirui et al. from the Cancer Hospital Chinese Academy of Medical Sciences published a study on nimotuzumab combined with chemoradiotherapy for the treatment of unresectable local advanced esophageal cancer ^[9]. The study included 26 newly diagnosed patients with esophageal cancer, with a median radiotherapy dose of 60 Gy, a median total nimotuzumab dose of 1200 mg, and an effective rate of 76.9%. The median follow-up was 30.5 months, and the median survival was 28.7 months. The 2-year and 3-year overall survival were 59.4% and 38.2%; the 2-year and 3-year progression-free survival were 51.4% and 33.3%. Another study conducted a retrospective analysis of the efficacy of nimotuzumab or cetuximab combined with chemoradiotherapy in the treatment of patients with locally advanced esophageal cancer ^[10]. The results showed that the ORR of the nimotuzumab + CRT group was 61%, slightly higher than that of the cetuximab + CRT group (43.5%), and the disease control rate of the nimotuzumab + CRT group was significantly higher than that of the cetuximab + CRT group ($P = 0.04$). Other survival analyses also showed that the median PFS of the nimotuzumab + CRT group was significantly longer than that of the cetuximab + CRT group (19.6 months vs 13.0 months, $p = 0.02$). The 1-year and 3-year OS of the nimotuzumab + CRT group were higher than those of the cetuximab + CRT group ($HR = 1.17$, $p = 0.23$).

At present, many studies have confirmed that nimotuzumab can improve the efficacy of esophageal cancer in the elderly. Common acute toxic reactions included esophagitis, pneumonia, leukopenia, gastrointestinal reactions, and thrombocytopenia. The incidence of Grade 3-4 adverse reactions was 17.4%, and no Grade 5 toxic reactions were observed. The median overall survival (OS) was 17 months, and the progression-free survival (PFS) was 10 months. The 2-, 3-, and 5-year OS and PFS were 30.4%, 21.7%, and 19.6%, and 26.1%, 19.6%, and 19.6%, respectively. This result confirms that nimotuzumab combined with radiotherapy is a safe and effective treatment for elderly patients who cannot undergo surgery. Li Lulu ^[11] randomly

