5.1 Inclusion criteria

Patients must meet all of the following criteria to be eligible for this trial:

- 1)The patients voluntarily participated in this study, signed the informed consent, had good compliance, and cooperated with the follow-up;
- 2)Age 75 and above, regardless of gender;
- 3)ECOG score 0-1;
- 4)Esophageal cancer confirmed by histology or cytology;
- 5)According to RECIST 1.1 (see 12.2. Response Evaluation Criteria for Solid Tumors Version 1.1 for details), there is at least one measurable lesion, and the measurable lesion should not have received local treatment such as radiotherapy (lesions located in the previous radiotherapy area can also be

selected as target lesions if they are confirmed to have progressed and meet the RECIST 1.1 criteria);

6)Patients with stage II-IVB according to AJCC (8th edition, 2018) (IVB included metastasis to the celiac trunk or supraclavicular lymph nodes only) who are not suitable for or refuse surgery can tolerate concurrent chemoradiotherapy and targeted therapy;

7)Expected survival time \geq 12 weeks;

8)The major organs function normally, that is, they meet the following criteria:

●Blood test:

- a.HBG \geq 90 g/L;
- b.ANC \geq 1.5×10^9 /L;
- c.PLT \geq 80×10^9 /L;

●Biochemical tests:

- a.ALB \geq 30 g/L;
- b.ALT and AST \leq 2.5 ULN; if there is liver metastasis, ALT and AST \leq 5 ULN;
- c.TBIL \leq 1.5ULN;
- d.Plasma Cr \leq 1.5ULN or creatinine clearance (CCr) \geq 60ml/min;

9)Echocardiographic assessment: left ventricular ejection fraction (LVEF) \geq lower limit of normal value (50%);

10)Female of childbearing age must agree to use contraceptive measures (such as intrauterine devices, birth control pills or condoms) during the study and within 6 months after the end of the study; the serum or urine pregnancy test is negative within 7 days before study enrollment, and they must be non-breastfeeding patients; men must agree to use contraceptive measures during the study and within 6 months after the end of the study.

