9.3 Statistical Analysis

9.3.1 Statistical analysis plan

SPSS version 26.0 software was used for statistical analysis. Baseline data were analyzed according to the full analysis set, and all efficacy indicators were analyzed according to the full analysis set and the per-protocol set; safety analysis was performed using the safety analysis set.

Descriptive statistics were used to analyze all data, including demographic data, baseline, various efficacy evaluation indicators, and all safety data. Measurement data were expressed as mean \pm standard deviation or median and upper and lower quartiles, and count data were expressed as frequency or percentage. Dropout was defined as any reason that caused the subject to fail to complete the follow-up required by the protocol. For exclusion, dropout cases were statistically described one by one. The anti-tumor efficacy of nimotuzumab was analyzed in the full analysis set and the per-protocol set.

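### The 16-month PFS benchmark in 9.1 is radiotherapy in inoperable squamous disease, so exceeding it supports a claim about the three-part regimen, not the efficacy of nimotuzumab named in 9.3.1 and 1.1

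*Protocol*

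**What the plan says.** **Benchmark.** Protocol 9.1 introduces the null value with "Based on previous studies on radical radiotherapy for elderly esophageal cancer" and states that "the median PFS of elderly patients with locally advanced and inoperable esophageal squamous cell carcinoma after radical radiotherapy was 16 months". It gives no citation and does not mention chemotherapy. The target follows: "It was estimated that the median PFS of this study could reach 18.2 months". A one-sided test at 0.05 with 80% power is set on this pair of medians.

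**Treatment.** Sections 4.1 and 6.1.2 give every patient radiotherapy, S-1 and nimotuzumab. There is no control arm.

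**Population.** Section 5.1, criterion 4, asks only for "Esophageal cancer confirmed by histology or cytology". Criterion 6 admits stages II to IVB (IVB limited to celiac trunk or supraclavicular nodes) in patients "who are not suitable for or refuse surgery". Criterion 2 sets the age at 75 and above.

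**Claim.** The title and purpose in 1.1 and the main purpose in section 3 name nimotuzumab combined with concurrent chemoradiotherapy. The study overview in 1.1, in contrast, says the trial explores the efficacy and safety of nimotuzumab. Section 9.3.1 says: "The anti-tumor efficacy of nimotuzumab was analyzed in the full analysis set and the per-protocol set".

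**The concern.** The benchmark and the trial differ in three ways that the protocol itself states: treatment (two drugs are added, not one), histology (squamous only against any) and operability (inoperable against unsuitable or refusing). Nothing in 9.1 adjusts the 16 months for any of them.

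With one arm, the test compares a whole package with an external number. If the result is then reported as the anti-tumor efficacy of nimotuzumab, the one-sided 5% error rate does not protect that statement. It would do so only if S-1 and the case mix left the 16-month median unchanged. The plan gives no ground for assuming that, and the effect it hopes to see is small enough that a modest shift would match or cancel it.

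**Working it through.** **1. Setting the texts side by side**

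| | Benchmark (9.1) | Trial (4.1, 5.1, 6.1.2) |
|---|---|---|
| Treatment | radical radiotherapy | radiotherapy + S-1 + nimotuzumab |
| Histology | squamous | any confirmed esophageal cancer |
| Surgery | inoperable | unsuitable or refusing |
| Stage | locally advanced | II to IVB |
| Age | elderly, cut-off not given | 75 and above |

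The first three rows are mismatches on the face of the text. In the last two, the benchmark is not described closely enough to compare.

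**2. The plan's own figures.** Inputs from 9.1: medians 16 and 18.2 months, one-sided 0.05, power 0.80, 41 cases, 52 after 20% dropout.
- Targeted gain: 18.2 − 16 = 2.2 months. Under exponential PFS the hazard ratio is 16/18.2 = 0.879, a 12% lower hazard.
- Dropout step: 41/0.8 = 51.25, rounded up to 52. This reproduces.
- The 41 does not reproduce. Events needed = (1.645 + 0.842)² / [ln(16/18.2)]² = 6.18/0.0166, about 373. This is a separate defect. It matters here only because it keeps power low.

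**3. How far the test protects a statement about nimotuzumab.** Assume that nimotuzumab adds nothing and that radiotherapy plus S-1 in this case mix has true median *m*. The values of *m* are assumptions; the documents give none. With n = 52 and exponential PFS:

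P(reject 16 months) = Φ( √(n·p) · ln(m/16) − 1.645 )

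Here p is the probability of an observed event. With λ = ln 2/m it is
- for 12 months' accrual plus 24 months: p = 1 − [exp(−24λ) − exp(−36λ)]/(12λ);
- for a fixed 24 months per subject: p = 1 − 0.5^(24/m).

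Example, m = 18.2, first version: p = 0.678; √(52 × 0.678) = 5.94; 5.94 × 0.1288 − 1.645 = −0.88; Φ = 0.19.

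| Assumed *m* (months) | 16 | 17 | 18.2 | 20 | 22 | 24 |
|---|---|---|---|---|---|---|
| 12 + 24 months | 5% | 10% | 19% | 36% | 56% | 72% |
| fixed 24 months | 5% | 10% | 18% | 33% | 51% | 66% |

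Using the 50 patients of section 1.1 instead of 52 changes the 18.2-month entry in the first row only from 18.9% to 18.5%.

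**4. The opposite direction.** If S-1 and case mix together put the background median at 16 × 16/18.2 = 14.1 months, a nimotuzumab effect of the full planned size (ratio 18.2/16 = 1.1375) brings the regimen to 16.0 months. The test then rejects 5% of the time although the drug works as hoped. The mismatch can therefore hide an effect as well as mimic one.

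**The case against.** **The regimen is already the question.** The title, the purpose in 1.1, the main purpose in section 3 and the design in 4.1 all name the combination, and 9.1 calls the study exploratory. The sentence in 9.3.1 mainly assigns analysis sets and draws no conclusion. This is largely right, and it limits the point to a conflict of wording plus an unmatched benchmark. It does not remove the conflict: 9.3.1 and the overview name nimotuzumab as what is being evaluated.

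**Single-arm phase II trials always lean on historical values.** True. The issue is a benchmark that differs in treatment, histology and operability, together with attribution to one of two added drugs.

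**The mismatch may be small.** Section 2.1 puts squamous carcinoma at 80% of cases worldwide and describes it as the main type in China, so few other histologies may be enrolled. The radiotherapy studies behind the 16 months may also have included chemotherapy; the protocol does not say. Both points stand as unknowns, and they are why no size of bias is claimed.

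**A subset analysis belongs in the SAP.** It may be placed there. The benchmark, the eligibility and the attribution wording are fixed in this protocol.

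**Stronger readings that the text does not support.** A reader might infer that the result says nothing about nimotuzumab. That goes too far: it describes a regimen containing nimotuzumab, and only the separate contribution is not identified. A reader might take the elderly series in 2.2, where "the progression-free survival (PFS) was 10 months", as proof that the benchmark turns on patient mix. That series received nimotuzumab plus radiotherapy in patients who could not undergo surgery, and 2.2 gives no histology or stage mix for it, so the gap to 16 months may reflect treatment, assessment, era or chance. A reader might also infer an easy win from fitter, earlier-stage patients. Entry runs to stage IVB and starts at age 75, and the benchmark's stage and age mix are not given, so no direction can be derived.

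**Conclusion.** The point holds in a limited form. As 9.1 is written, a PFS above 16 months can support a statement about nimotuzumab plus S-1 plus radiotherapy against a radiotherapy benchmark, and no more. The wording in 9.3.1 and the overview sentence in 1.1 exceed what the design can show and conflict with section 3.

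The margin is thin. A combined S-1 and case-mix effect of 12% on the hazard equals the whole targeted gain in true median. That is a statement about the true median, not about the test: at n = 52 a true median of 18.2 months rejects 16 months only 18 to 19% of the time. The chance of a significant result with no nimotuzumab effect rises above the nominal 5% to 33–36% if the background median is 20 months, and falls below 5% if it is under 16.

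These figures rest on exponential PFS, the stated accrual and follow-up, and assumed background medians. The enrolled mix and the benchmark's composition are unknown, so neither the size nor the direction of any actual bias can be given.

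**What to change.** 1. In 1.1, 9.1 and 9.3.1, state that the comparison is of nimotuzumab plus S-1 plus radiotherapy against a radiotherapy benchmark. Replace *efficacy of nimotuzumab* with *efficacy of the regimen*, in line with section 3.
2. Beside the all-subject estimate, report median PFS with its confidence interval in squamous patients unsuitable for surgery, descriptively and without a further test. Say in the text that this subset matches the benchmark on histology and operability only and leaves the S-1 difference in place.

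The subset can be identified when inclusion criteria 4 and 6 are checked. The screening list in 4.1.1 does not name histological type or the reason for no surgery, so the CRF should record both.

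Cost: a wording change, two recorded items and one descriptive estimate. Eligibility, treatment and enrolment are untouched. The downside is a narrower claim and a wide interval in the subset.

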1.1 Summary

[figure not shown]
Title:	A single-arm, prospective, single-center phase II clinical study to evaluate the efficacy and safety of nimotuzumab combined with concurrent chemoradiotherapy in elderly patients with locally advanced unresectable esophageal cancer
Study overview	The mortality rate of esophageal cancer is 77%, and this rate will be even higher in elderly patients with esophageal cancer. A safe and effective treatment method is urgently needed. Currently, Nimotuzumab has been approved for esophageal cancer indications in 9 countries. We plan to conduct a single-arm, prospective, single-center Phase II clinical study to explore the efficacy and safety of Nimotuzumab in elderly patients with locally advanced esophageal cancer. The study population is elderly patients with locally advanced unresectable esophageal cancer, and 50 people are planned to be enrolled.
Purpose	To evaluate the efficacy and safety of nimotuzumab combined with concurrent chemoradiotherapy in elderly patients with locally advanced unresectable esophageal cancer.
Endpoint	Primary endpoint: progression-free survival (PFS) Secondary endpoints: objective response rate (ORR), disease control rate (DCR), local disease control rate (LDCR), overall survival (OS), 1-year OS/PFS, 2-year OS/PFS, and AE/SAE incidence.
Study population	Inclusion criteria: All the following patients must be met to be included in this study 1.The subjects voluntarily participated in this study, signed the informed consent, had good compliance, and cooperated with the follow-up; 2.Age 75 and above , male or female;

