Study intervention	
1.Radiation Therapy
 
The prescription dose required that 95% PTV and PTV-nd receive 50-60 Gy /25-30 F , with a single dose range of 2.0 Gy/F, 5 days a week, external beam radiation to the chest .
 
2.Treatment
 
S-1: 40-60 mg/m² , po, D1, BID, 5 weeks;
 
Nimotuzumab 400 mg, iv, D1, week 1;
 
Nimotuzumab 200 mg, iv, D8, QW, Week 2-5.

Study duration	The estimated time from the start of the study to the completion of data analysis is 40 months
Visit duration	The planned enrollment period for this study is 12 months, and the time required for each subject to complete all visits are 24 months.

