9.3.2 Effectiveness Analysis

Kaplan-Meier curves were drawn to estimate the survival rate, median survival time, and hazard ratio.

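### The stated 41 cases give about 16–22% power, not 80%, for a median PFS of 18.2 against 16 months; the planned total is also 50 in one place and 52 in another

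*Protocol*

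**What the plan says.** Section 9.1 bases the sample size on investigator-assessed PFS. It takes a median of 16 months after radical radiotherapy in elderly patients, from earlier studies that it does not cite. For this trial, "It was estimated that the median PFS of this study could reach 18.2 months". With a one-sided test at alpha 0.05 and "power=0.80, the sample size was calculated to be 41 cases", it allows for 20% dropout and concludes that "a total sample size of 52 subjects was required". It names no test statistic and no survival distribution.

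The Summary (section 1.1) gives a different total: "50 people are planned to be enrolled". On timing it says "The planned enrollment period for this study is 12 months", that each subject's visits take 24 months, and "The estimated time from the start of the study to the completion of data analysis is 40 months".

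On analysis, section 9.3.1 is descriptive, and 9.3.2 says "Kaplan-Meier curves were drawn to estimate the survival rate, median survival time, and hazard ratio". Neither states a test against 16 months.

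**The concern.** The two medians differ by 2.2 months, a hazard ratio of 16/18.2 = 0.879 under exponential PFS. Separating medians that close normally takes hundreds of events, so 41 cases with 80% power looked implausible on sight.

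This calculation is the only justification the protocol gives for its size. Someone relying on it would believe the risk of missing a true median of 18.2 months is 20%, when it is nearer 80%. The two enrolment totals add a plain contradiction about how many patients the trial needs.

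**Working it through.** **Inputs.** From section 9.1: null median 16 months, target 18.2 months, one-sided alpha 0.05, power 0.80, 41 cases, 20% dropout. From the Summary: 12 months' accrual, 24 months of visits per subject, 40 months to completed analysis. My assumptions, since the protocol names none: exponential PFS and uniform accrual.

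**1. Trying to reproduce 41.** Events for a single-arm test of a rate against a fixed value:

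d = [(z₀.₉₅ + z₀.₈₀) / ln(18.2/16)]² = [(1.6449 + 0.8416) / 0.12883]² = **372.5**

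Other standard forms do not give 41 either:
- an exact chi-square test needs 368 events;
- linear and square-root rate scales need 327 to 423;
- a two-sided test needs 473;
- a binomial test of the PFS rate at 12, 16, 18.2 or 24 months needs 641 to 990 patients;
- a two-arm log-rank formula needs about 1,490 events.

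**2. Patients needed for 80% power.** With a median of 18.2 months, the hazard is λ = ln 2/18.2. For a fixed 24 months each, P(event) = 1 − exp(−24λ). For 12 months' accrual plus f further months, P(event) = 1 − [exp(−λf) − exp(−λ(f+12))]/(12λ). Then N = 372.5/P(event).

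**3. Power with 41 patients.** Power = Φ(0.12883·√d − 1.645), with d = 41 × P(event). The exact column uses the chi-square test with d rounded.

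| Follow-up | P(event) | N for 80% | Events from 41 | Power, normal | Power, exact |
|---|---|---|---|---|---|
| 24 months each | 0.599 | about 622 | 24.6 | 15.7% | 17.2% |
| 12 accrual + 24 | 0.678 | about 550 | 27.8 | 16.7% | 18.1% |
| 12 accrual + 28 | 0.724 | about 515 | 29.7 | 17.3% | 18.7% |
| Event in all 41 | 1 | – | 41 | 20.6% | 22.1% |

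The 12 + 28 row is an upper bound, because the 40 months include data analysis. Simulating a one-sample log-rank test (60,000 runs) gave 14–19% over the three timelines, depending on the variance form. Even 52 patients, all with an event, reach only 24–25%.

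**4. Precision.** The 95% interval around 18.2 is 18.2 × exp(±1.96/√d). With 24.6 events it is 12.3 to 27.0 months; with 27.8 events, 12.6 to 26.4. Both contain 16.

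**5. What 41 patients could support.** Changing one input at a time:
- Target against 16 months: solve √(41·P(m)) × ln(m/16) = 2.486. This gives 23.6 months if all 41 have an event, 26.6 (12 + 28), 27.2 (12 + 24, about 22 events) or 28.7 (24 months each). The simulated log-rank test is already at 83–86% power at 27.2 months on 12 + 24, so the median with 80% power there is about 26 to 27, depending on the test.
- Null against 18.2 months: 12.3 months with all events, 11.0 to 11.5 on the three timelines.
- Distribution: a Weibull shape of about 3.0 with all events, or 3.1 on 12 + 24.

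**6. Enrolment total.** 41/(1 − 0.20) = 51.25, which rounds up to 52, so that step in 9.1 is right. The Summary's 50 leaves 50 × 0.80 = 40, one short of 41. Multiplying instead, 41 × 1.2 = 49.2, would give 50, but the protocol does not say where 50 comes from.

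**The case against.** The strongest technical defence is the distribution. The power figures assume exponential PFS, and a Weibull shape near 3 with nearly all events observed would yield 41. Nothing in the protocol supports that. Shapes of 1.5 and 2 give only 34% and 50% power even with 41 events. The elderly series in section 2.2 points the other way: with a median of 10 months and 26.1% progression-free at two years, the implied shape is ln[−ln(0.261)/ln 2]/ln(24/10) = 0.76, and its curve is flat at 19.6% from three to five years. A shape of 0.7 gives about 14% power with all events observed.

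The second defence is purpose. Section 9.1 itself says "This study is a single-arm, prospective, exploratory, single-center phase II clinical study", and 9.3 is descriptive, with no success threshold. This stands in part. In this protocol the fault is a misleading justification, not a faulty decision rule. But 9.1 still claims a one-sided test with 80% power, and an exploratory label does not make that claim true. Nor can a separate analysis plan make 41 cases deliver it.

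Two smaller points are fair. A difference of two patients between the totals is minor on its own. And because the source of the error is unknown, the protocol alone does not show whether a median, the power or the number of cases is the figure to correct.

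**Conclusion.** The point holds, and 9.1 must be corrected. Under exponential PFS and uniform accrual, 41 patients give about 16–19% power on the stated timelines and 21–22% at the very most, against the 80% claimed. The event requirement is understated about ninefold (372 against 41). The conclusion does not depend on the choice among standard tests; only an unstated and unsupported distribution would rescue it. The conflict between 50 and 52 needs no assumption at all.

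**What to change.** Recover the inputs and method behind 41 (null median, target median, test, assumed distribution), correct whichever is wrong, and cite the source of the 16 months.

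If 16 and 18.2 months both stand, replace the 80% claim with wording such as:

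> Under exponential PFS with 12 months' accrual and 24 months' further follow-up, 41 patients give about 17% power (one-sided alpha 0.05) if the true median is 18.2 months (about 28 events; expected 95% CI about 12.6 to 26.4 months). Power reaches 80% only if the true median is about 26 to 27 months, depending on the test (about 22 events).

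In that case, present the trial as estimating median PFS with a confidence interval. Give one enrolment total in the Summary and in 9.1; 52 is the figure that follows from 41 and 20% dropout.

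The cost is rewording two sections. The trial need not be enlarged beyond the size 9.1 already states, but its stated power becomes far less favourable and it can claim only estimation with a wide interval.
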